To describe in each study group the incidence of RSV LRTI hospitalization and all-cause LRTI hospitalization in UK reconsented participants from D366 to D731	 Incidence of RSV LRTI hospitalization Incidence of hospitalization for all-cause LRTI 				

Overall Design

Type of design	Open-label, multi-center, parallel 2-arm study: nirsevimab compared to no preventive RSV intervention					
Phase	IIIb					
Control method	Comparison to no preventive intervention					
Study population	Healthy infants born ≥ 29 weeks gestational age (WGA) entering their first RSV season and not eligible for palivizumab (born either in-season or out-of-season)					
Countries	France, Germany, and the United Kingdom					
Level and method of blinding	Open-label					
Study intervention assignment method	 Randomization will be stratified by the following: Country Age group at time of randomization (ie, age ≤ 3.0 months, age > 3.0 to ≤ 6.0 months, age > 6.0 months) 					

Brief Summary

The purpose of this study is to determine the efficacy and safety of a single intramuscular (IM) dose of nirsevimab, compared to no intervention, for the prevention of hospitalizations due to

LRTI caused by confirmed RSV infection (henceforth referred to as RSV LRTI hospitalizations) in all infants under 12 months of age who are not eligible to receive palivizumab.

Study Duration: 12 months post-dosing/randomization for France, Germany, and UK non-reconsented participants, 24 months post-dosing/randomization for UK reconsented participants. D01 will be the day of randomization (both study groups) and immunization (nirsevimab group).

Treatment Duration: 1 IM injection

Study Calendar:

- Planned date of first participant in: 01 September 2022
- Planned date of last participant in: 28 February 2023
- Planned date of last visit last participant: 28 February 2025

Note: As much as operationally feasible, the date of inclusion of the first participant will be aligned with the beginning of the RSV season. It is thus possible that the first participants are enrolled earlier than 01 September 2022.

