In order to minimize the burden on sites, families and participants, while still answering the objective of this protocol amendment, it was decided to invite in the study extension only the UK participants, who represent 50% of the study population.

Enrollment of Study Participants

A total of 28 860 participants will be enrolled from sites in France, Germany, and the United Kingdom. The study will enroll infants born either out of the RSV season or in the RSV season.

Definition of the RSV season

There is an important variability of RSV seasonality from year to year in each country. The typical RSV season in the Northern Hemisphere (NH) last approximately 5 months and usually starts in October or November. Therefore, the "Out-of-Season" period refers to the approximately 7 months period from March or April to September or October. The actual start date and length of the RSV season will depend on the actual circulation of RSV in the NH in 2022.

Cases of LRTI hospitalization will be collected throughout the study to ensure that all cases occurring during the next RSV season are captured. For the need of this study, the start and end dates of the RSV season will be defined on a country-by-country basis and will be based on country-specific epidemiological surveillance. For the mothers of infants to be born in-season, recruitment will start at 30 weeks gestation in women with an estimated delivery date during the RSV season.

Rationale for the Collection of Safety Data

Immediate AEs

As nirsevimab is not a marketed product, a 30 minutes immediate surveillance period of infants enrolled in the nirsevimab group will be done on the site where immunization was performed.

Non-serious AEs

For a period of 30 days post-dosing/randomization, non-serious AEs will be captured in the eCRF for all study participants. The relation of AEs to interventional product will be determined by the Investigator.

The use of the eDiary by parents and the process for reporting AEs in the eCRF is outlined in Section 8.2.3.

Hospitalizations

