8.1.2.1 Definitions

"Hospitalization" is defined as the decision to admit to in-patient care by the treating physician.

"RSV season" is the period of increased RSV infection. For the purpose of efficacy analyses, the start and end dates of the RSV season will be defined on a country-by-country basis and will be based on country-specific epidemiological surveillance.

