2.4. Primary Efficacy Variable

The primary efficacy variable is the overall incidence of RSV LRTI hospitalization through the RSV season.

“Hospitalization” is defined as the decision to admit to in-patient care by a physician.

“RSV season” is the period of increased RSV infection. For the purpose of efficacy analyses, the start and end dates of the RSV season will be defined on a country-by-country basis and will be based on country-specific epidemiological surveillance. Methodology to define the season will be agreed upon with the National Core Investigators (NCI) and described in detail. Methodology will depend on RSV circulation, hence, an a priori definition is not possible due to the impact of COVID and related public health measures.

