 - for the participants who had no contact for safety events at all throughout the efficacy follow-up period, the end date for the efficacy follow-up will be date of randomization for participants who are randomized to no intervention, the date of treatment dosing for participants who are randomized to nirsevimab and treated, and the date of randomization for participants who are randomized to nirsevimab but not treated.

The total person-time for the follow-up time of each participant will be calculated as:

Person-months = (the end date - the start date + 1)/30.4375.

NN (days), the total person-time contributed by participants randomized in the nirsevimab, will be the sum of person-months for all the participants in the nirsevimab group. And NC (days), the total person-time contributed by participants randomized in the no intervention group, will be the sum of person-months for all the participants in the no intervention group.

The 2-sided 95% CI for the efficacy will be calculated by an exact method assuming a binomial distribution of the number of RSV LRTI hospitalizations in the nirsevimab group conditional on the total number in both groups (described by Breslow and Day⁷) accounting for the follow-up time post-dosing/randomization.

The superior efficacy of nirsevimab in preventing RSV LRTI hospitalization is concluded if the lower bound of 2-sided 95% CI of the efficacy is $> 0\%$. P-value will also be provided. The primary efficacy analysis of the primary endpoint will be performed with the All Randomized Set.

RSV season is the period of increased RSV infection. For the purpose of efficacy analyses, the start of the RSV season will be defined on a country-by-country basis and will be based on country-specific epidemiological surveillance and the cut-off date (28Feb2023, except for site parent contact and medical call center contact, for which the date of database lock for Primary Analysis will be used) will be used as end dates.

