6.6.7.10. Rerun of Primary Analysis at the Time of First Year Analysis

The Primary Analysis will be re-run at the time of the First Year Analysis considering the same cut-off date and the same rules as the Primary Analysis.

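### SAP 6.6.1 sets the RSV season end at the 28 February 2023 data cut-off, so no planned through-season analysis uses the surveillance-defined end that the protocol and SAP 2.4 specify

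*SAP*

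**What the plan says.** Protocol 8.1.2.1 states that "the start and end dates of the RSV season will be defined on a country-by-country basis and will be based on country-specific epidemiological surveillance". Protocol 2.2 and 4.2 say the same, and SAP 2.4 repeats that "the start and end dates of the RSV season will be defined on a country-by-country basis", adding that the method will be agreed with the National Core Investigators and described. Protocol 4.2 gives the purpose of the long collection period: "Cases of LRTI hospitalization will be collected throughout the study to ensure that all cases occurring during the next RSV season are captured".

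The operative text in SAP 6.6.1 differs. It says "For the purpose of efficacy analyses, the start of the RSV season will be defined on a country-by-country basis", dropping the end date from that basis, and then that the cut-off of 28 February 2023, "except for site parent contact and medical call center contact, for which the date of database lock for Primary Analysis will be used) will be" taken as the season end. The very severe and by-country analyses (SAP 6.6.4.1, 6.6.4.2) use the same follow-up algorithm. The all-cause LRTI through-season analysis (6.6.4.3.1) uses the primary analysis method. The First Year re-run in SAP 6.6.7.10 is done "considering the same cut-off date and the same rules as the Primary Analysis". The synopsis calendar gives the same date as the close of enrolment: "Planned date of last participant in: 28 February 2023".

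**The concern.** The primary, both key secondary and one all-cause LRTI objective ask about protection over the RSV season. Under SAP 6.6.1 they are answered up to a fixed administrative date. A cut-off for the Primary Analysis alone would be unremarkable. The difficulty is that the cut-off becomes the season end and so carries forward into the First Year results. Wherever a country's season outlasted 28 February, the stated question has no planned answer.

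Two groups are affected most. Infants enrolled late, including the in-season newborns whom the trial sets out to recruit, contribute very little follow-up. Infants dosed early lose the part of the season when they are furthest from dosing.

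**Working it through.** **The plan's own figures.** Protocol 9.2 and SAP 2.3 assume a 1.1% control rate, 60% efficacy (hence 0.44%) and 9,620 infants per country, or 4,810 per arm. Expected events are 4,810 × (0.011 + 0.0044) = 74.07, matching the stated 74. With the exact conditional binomial (null 0.5, alternative 0.4/1.4 = 0.286), 74 events give 91.4% power at two-sided 1.66%, and 61 events give 92.2% at two-sided 5%. These reproduce. No season end date enters them, and the fix does not alter them.

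**The text, step by step.**
1. SAP 5.2.1 has two censoring rules. At the Primary Analysis, follow-up ends at the earliest of season end, last confirmed event-free date and cut-off. At the First Year Analysis it ends at the earlier of last confirmed date and season end, with no cut-off.
2. The two rules differ only if the season can outlast the cut-off. SAP 6.6.1 makes the two dates equal, so the difference disappears.
3. The re-run in 6.6.7.10 keeps the same date. No through-season analysis is left that uses a surveillance-defined end.
4. The database-lock exception concerns contact dates. It does not restore a surveillance-based season end.
5. For participants with the endpoint, SAP 6.6.1 uses the admission date only when the cut-off falls before the season end. With the two dates equal, that condition is never met. Read literally, cases are censored at the season end, whereas protocol 9.4.2 ends their follow-up at admission.

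**Size.** Inputs are a typical season of about 5 months starting in October or November (protocol 2.2, 4.2) and planned enrolment from 1 September 2022 to 28 February 2023 (synopsis), which is 181 dates. Uniform enrolment is an assumption.

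Let A be the days from season start to 28 February inclusive, and L the days from 1 March to season end. Then 181 − A enrolment dates fall before the season.
- In-season person-days kept (one infant per date) = (181 − A) × A + A(A + 1)/2.
- Person-days lost = 181 × L, because every enrolment date precedes the season end.
- Share lost = 181L / (kept + 181L).

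| Start | End | A | L (share of 151 season days) | Kept | Lost | Share lost |
|---|---|---|---|---|---|---|
| 1 Oct | 28 Feb | 151 | 0 (0%) | 16,006 | 0 | 0% |
| 15 Oct | 14 Mar | 137 | 14 (9%) | 15,481 | 2,534 | 14% |
| 1 Nov | 31 Mar | 120 | 31 (21%) | 14,580 | 5,611 | 28% |
| 15 Nov | 14 Apr | 106 | 45 (30%) | 13,621 | 8,145 | 37% |
| 30 Nov | 29 Apr | 91 | 60 (40%) | 12,376 | 10,860 | 47% |

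For 1 November: 61 × 120 + 120 × 121/2 = 7,320 + 7,260 = 14,580 kept; 181 × 31 = 5,611 lost; 5,611/20,191 = 28%.

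Counting all days from enrolment, mean follow-up at 28 February is (1 + 181)/2 = 91 days. About 30/181 = 17% of infants have 30 days or less and 60/181 = 33% have 60 days or less. An infant enrolled on the last day contributes one day.

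**The case against.** Several points on the other side stand.

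- **A cut-off is in the protocol.** Sections 9.4.1 and 9.4.2 estimate efficacy up to the Primary Analysis cut-off, triggered at 61 events or more and no later than 30 April 2023. A confirmatory result short of a full season was therefore accepted. What remains is the redefinition of season end and the missing later analysis.
- **The season may have ended by then.** A reader might infer that efficacy is never analysed through the season. The documents do not show this. They give no 2022-23 end date, and a 5-month season starting on 1 October ends on 28 February. A season that ended earlier would be overrun, not truncated.
- **Later events are not discarded.** LRTI hospitalizations are collected to D366 and enter the Day 151, Day 181 and Day 181-366 analyses. For an infant enrolled on 1 September, Day 181 is 28 February; for one enrolled on 2 October it is 31 March. These are nevertheless descriptive windows counted from dosing or randomization, and they do not estimate efficacy over a calendar season.
- **No bias in the test is shown.** A reader might infer that the cut-off favours one arm. The same calendar date applies to both 1:1 randomized arms, and the rate-based method accounts for follow-up time.
- **The choice is not hidden.** SAP 6.6.1 states the date, and the SAP document history records the decision. Section 7, where departures from the protocol's planned analysis belong, does not.

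**Conclusion.** The conflict is in the current text and holds without inference: SAP 6.6.1 contradicts the protocol and SAP 2.4 on how the season ends, and no planned through-season analysis uses a surveillance-defined end. The consequence is for labelling and generalizability. The validity of the confirmatory superiority test is not affected.

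The size depends on when each country's season ended, which the documents do not give. Under the typical season described in the protocol and assumed uniform enrolment, 0% to 47% of in-season person-time is cut, 28% for a 1 November start. A simple count from enrolment for that start gives 31/122 = 25%, but its denominator includes September and October pre-season days, so it should not be read as a share of season person-time. Lost person-time is also not lost events; no event loss is estimated here. In any country whose season ended on 28 February the loss is nil.

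The end-date condition for cases is a separate wording defect. It holds whatever the true season dates were.

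**What to change.** 1. Reconcile SAP 6.6.1 with SAP 2.4 and the protocol on the season end, and list the change in section 7.
2. Label the Primary Analysis results, and their First Year re-run, as covering randomization (or dosing) to 28 February 2023.
3. Add a descriptive, non-confirmatory exact analysis with 95% CIs for RSV LRTI hospitalization (overall and by country), very severe RSV LRTI and all-cause LRTI hospitalization, with follow-up ending at each country's surveillance-defined season end. Report the dates used and the method agreed with the National Core Investigators.
4. Run it with the Second Year outputs and label it post hoc. SAP section 7 reports the First Year re-run as already done, and SAP 6.6.9 sets a precedent with a post hoc endpoint that has a fixed calendar end and is run at that stage.
5. Correct the rule for cases in SAP 6.6.1 so that follow-up ends at hospital admission, as in protocol 9.4.2.

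The cost is SAP wording and one extra descriptive re-run on LRTI data already collected to D366. The confirmatory test and alpha are unchanged. The drawback is that the season-end estimates carry a post hoc label.

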6.6.2. Sensitivity Analyses for the Primary Objective

6.6.2.1. Analyses with Poisson Regression Model

A sensitivity analysis using a Poisson regression model with robust variance will be performed on All Randomized Set. The model will contain the following independent variables: the term of treatment group (ie, nirsevimab, no intervention), and age group at randomization (ie, $\text{age} \leq 3.0$ months, $\text{age} > 3.0$ to ≤ 6.0 months, $\text{age} > 6.0$ months), and country (ie, France, Germany and United Kingdom) as covariates, adjusting for the log of the follow-up time of the first event as an offset. No interaction terms will be included in the model. The efficacy of nirsevimab in preventing RSV LRTI hospitalization, defined as $(1 \text{ minus the incidence rate ratio}) \times 100\%$ and its corresponding 2-sided 95% CI will be estimated from the model by exponentiating the poisson model coefficients. Follow-up time for the log offset will be calculated as per Section 6.6.1. P-value will be provided.

6.6.2.2. Tipping-Point Analysis

Due to the open-label nature of the study, an excess of withdrawals might be observed in the no intervention group and be translated into a biased estimator when assuming the non-informative censoring hypothesis.

In order to test this hypothesis, a tipping point analysis^{8,9,10} will be performed to assess the impact of imputating missing data under a various range of hypotheses.

1. In order to perform the tipping point analysis, data will be imputed for all participants with missing data, (ie who discontinued the study, or with a RSV test equals to missing or Not Done) from both groups, several scenarios will be evaluated:
 - a. Best case scenario: no RSV LRTI hospitalization among the missing data in nirsevimab group whereas all missing data in the no intervention group will be imputed as RSV LRTI hospitalization.
 - b. Worst case scenario: all missing data in nirsevimab group will be imputed as RSV LRTI hospitalization whereas no missing data in the no intervention group will be imputed as RSV LRTI hospitalization.
 - c. The number of RSV LRTI hospitalizations imputed in each arm will be incremented from 0% (complete case analysis with no RSV LRTI hospitalization imputed in any arm), by 10%, to the total number of missing data in each arm. Remaining participants with missing data (from 90% of total number of missing data to 0%) will be then imputed as having no RSV LRTI hospitalizations.
2. For each combination:
 - a. Person-months will be imputed in both treatment groups using the overall distribution of person-months in the respective group for non-missing participants. The following values will be considered and evaluated as different scenarios: minimum value, Q1, Q2, Q3 and maximum value.
 - b. Corresponding Incidence Rates will be imputed in each treatment arm.
 - c. For non aggregated rows, Efficacy for participants with missing data will be provided

$$\text{Eff}_{\text{miss}} = 100 \times \left(1 - \frac{\text{Incidence Rate Miss Nirsevimab}}{\text{Incidence Rate Miss No Intervention}} \right) = 100 \times \left(1 - \frac{\text{IRN}_{\text{Miss}}}{\text{IRC}_{\text{Miss}}} \right)$$

- d. For non aggregated rows, Overall Efficacy will also be computed with its 2-sided 95% Confidence Interval (described by Breslow and Day as for primary analysis) and corresponding p-value

$$\begin{aligned} \text{Eff}_{\text{Overall}} &= 100 \times \left(1 - \frac{\text{Incidence Rate Overall Nirsevimab}}{\text{Incidence Rate Overall No Intervention}} \right) = 100 \times \left(1 - \frac{\text{IRN}_{\text{Overall}}}{\text{IRC}_{\text{Overall}}} \right) \\ &= 100 \times \left(1 - \frac{\text{IRN}_{\text{Obs}} \times \text{Prop}_{\text{Obs}}^{\text{N}} + \text{IRN}_{\text{Miss}} \times \text{Prop}_{\text{Miss}}^{\text{N}}}{\text{IRC}_{\text{Obs}} \times \text{Prop}_{\text{Obs}}^{\text{C}} + \text{IRC}_{\text{Miss}} \times \text{Prop}_{\text{Miss}}^{\text{C}}} \right) \end{aligned}$$

With:

- ✓ IRN_{Obs} = Incidence Rate observed in nirsevimab group
 - ✓ IRC_{Obs} = Incidence Rate observed in No Intervention group
 - ✓ $Prop_{Obs}^N = \frac{NN}{NN+NN_{Miss}}$ = Proportion of observed person-time in nirsevimab group defined as
 - ✓ $Prop_{Obs}^C = \frac{NC}{NC+NC_{Miss}}$ = Proportion of observed person-time in No Intervention group defined as
 - ✓ $Prop_{Miss}^N = \frac{NN_{Miss}}{NN+NN_{Miss}}$ = Proportion of missing person-time in nirsevimab group defined as
 - ✓ $Prop_{Miss}^C = \frac{NC_{Miss}}{NC+NC_{Miss}}$ = Proportion of missing person-time in No Intervention group defined as
- e. Then, person-months imputed from these different scenarios in no intervention group (min, Q1, Q2, Q3, max) in step 2)a) will be aggregated by PROC MIANALYZE in SAS using Rubin's rule, for a same combination of percentages in step 1)c).
- f. Step 2)e) will be repeated 5 times for the same combination of percentages working on the person-months imputed in nirsevimab group (min, Q1, Q2, Q3, max).
- g. For a same combination of percentages in step 1)c), person-months imputed from the 25 different scenarios in both groups (min, Q1, Q2, Q3, max in nirsevimab group/ min, Q1, Q2, Q3, max in no intervention group) will be aggregated by PROC MIANALYZE in SAS.
- h. For each different aggregated row from steps 2)e), 2)f), 2)g), Overall Efficacy, corresponding 95% CI and p-value will be provided by PROC MIANALYZE in SAS.

In addition, a graphical representation of all efficacy results off complete aggregated rows (produced in step 2)g)) will also be provided.

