2.2 Background

RSV Seasonality

In much of the Northern Hemisphere, including the UK, France, and Germany, RSV infection is a clearly identified winter illness with most cases observed over a period of approximately 5 months that usually starts in October or November. Whilst the timeframe can vary slightly from year to year, this period of approximately 5 months is commonly referred to as the "RSV season" in this region. In this study, "RSV season" will be used to refer to this period of increased RSV infection. For the purpose of efficacy analyses, the start and end dates of the RSV season will be defined on a country-by-country basis and will be based on country-specific epidemiological surveillance. As a result of the COVID-19 pandemic, the seasonality of RSV has been modified (11). During 2020, the circulation of RSV was substantially reduced, presumably due to the widespread implementation of non-pharmacological interventions such as face mask use, increased handwashing practices, social distancing, and travel restrictions. This reduced circulation of RSV produced a larger-than-usual RSV-susceptible population.

RSV Infections Prevalence and Epidemiology

Lower respiratory tract infection due to RSV, characterized predominantly as bronchiolitis or pneumonia, can manifest with acute and sometimes long-term consequences for the developing lungs of young infants and children (12). It is estimated that RSV infections account for around 60% to 80% of infant bronchiolitis. In addition, RSV is one of the leading causes of pediatric pneumonia (up to 40% of pneumonias all causes in particular in infants and toddlers) (13).

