9.2 Sample Size Determination

A total of 28 860 participants are expected to be enrolled of whom approximately 14 430 will receive nirsevimab and 14 430 will receive no intervention. This sample size is driven by the

demonstration of efficacy in preventing RSV LRTI hospitalization in each of 3 countries independently.

Based on the reported incidence rates of RSV LRTI hospitalization in France, Germany, and the UK (2) (51) (52), assuming a 1.1% incidence rate on average in the control group (ie, receiving no intervention), 9620 participants need to be enrolled in each of the 3 countries (which is equivalent to 74 events of RSV LRTI in each country) to ensure the 90% power to detect 60% efficacy in each country with a 2-sided α of 1.66% taking the multiplicity adjustment using Bonferroni approach into consideration.

The sample size of 28 860 participants has at least 99% power to detect 60% efficacy in preventing RSV LRTI hospitalizations in all 3 countries combined assuming an incidence rate of 0.86% in the control group (the lowest reported in the 3 countries) with a 2-sided α of 5%, and approximately 95% power to detect 60% efficacy in preventing very severe RSV LRTI defined in the protocol assuming an incidence rate of 0.4% in the control group (59) with a 2-sided α of 5%. To ensure at least 90% power for very severe RSV LRTI, at least 61 events are needed.

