6.6.5.1.2. Tipping-Point Analysis

The same analysis as for the primary endpoint will be performed, imputing for all participants with missing data (ie who discontinued the study, or with a RSV test equals to missing or Not Done, or with missing oxygen saturation, or with missing oxygen supplementation) from both groups.

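### The tipping-point grid has no step between 0% and 10% of missing infants and gives drop-outs and untested LRTI admissions one shared percentage, so it may not resolve where the result tips

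*SAP*

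**What the plan says.** SAP 6.6.2.2 introduces the tipping-point analysis because the open-label design may produce excess withdrawals in the no-intervention group and so biased censoring. The missing pool is defined as infants "ie who discontinued the study, or with a RSV test equals to missing or Not Done".

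Within each arm, the number imputed as RSV LRTI hospitalizations "will be incremented from 0% (complete case analysis with no RSV LRTI hospitalization imputed in any arm), by 10%, to the total number" missing in that arm, and the remainder are imputed as event-free. All combinations across arms are run, with best-case and worst-case rows at the corners. Imputed person-months are the minimum, quartiles and maximum of the non-missing infants in the same arm.

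SAP 6.6.5.1.2 reuses this for very severe RSV LRTI: "The same analysis as for the primary endpoint will be performed, imputing for all participants with missing data". There the pool also takes in missing oxygen saturation or oxygen supplementation. SAP 6.6.5.2.2 reuses it for each country with the Bonferroni-Holm adjustment.

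**The concern.** For drop-outs, the group that the SAP names as its worry, the relevant event probabilities are of the order of the planned incidences: 1.1% or 0.86% in control, 0.44% on nirsevimab at 60% efficacy, and 0.4% in control for very severe disease. The grid has one point in that region, 0%, and then jumps to 10%. If the result holds at 0% and fails at 10%, the analysis cannot tell a tip near 1% (fragile) from one near 9% (robust to any planned rate).

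An infant already admitted with LRTI but not tested is a different case. The protocol's background says that "RSV infections account for around 60% to 80% of infant bronchiolitis". That is only a rough guide, since the endpoint is LRTI and the same section gives up to 40% for pneumonia, but it is far from 1%. Percentages may differ between arms, but not between types of missingness within an arm, so any one value mixes a withdrawal question with a testing question.

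Recorded times are also set aside. Protocol 1.3 collects admission dates, and the censoring, cut-off and season-end dates are defined in SAP 3.1.4 and 6.6.1.

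**Working it through.** **Inputs.** From Protocol 9.2: 14 430 infants per arm, 4810 per arm per country, 60% efficacy (rate ratio 0.4), and control rates of 1.1%, 0.86% and 0.4%. From SAP 6.7.8: Primary Analysis at 61 or more events. Missing rates are not in the documents, so the values below are assumptions.

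**Plan's own figure.** Expected events per country are 4810 × (0.011 + 0.0044) = 74.1. Freedman's formula at two-sided alpha 1.66% and 90% power gives (1.4/0.6)² × (2.395 + 1.282)² = 5.444 × 13.52 = 73.6, so 74. The stated 74 is reproduced.

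**Size of the first step.** 10/1.1 = 9.1; 10/0.86 = 11.6; 10/0.44 = 22.7; 10/0.4 = 25.

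**Planned event counts, nirsevimab v control.**
- Primary at 1.1%: 14 430 × 0.0044 = 63 v 14 430 × 0.011 = 159.
- Primary at 0.86%: 50 v 124.
- One country: 4810 × 0.0044 = 21 v 4810 × 0.011 = 53.
- Very severe: 14 430 × 0.0016 = 23 v 14 430 × 0.004 = 58.
- At the 61-event trigger: 61 × 0.4/1.4 = 17 v 44.

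**Tipping rule.** With x nirsevimab events out of D and equal person-time, the exact upper limit for the nirsevimab share is p_U = Beta⁻¹(1 − α/2; x + 1, D − x). The lower efficacy limit is 1 − p_U/(1 − p_U). Add k events to nirsevimab and none to control until this limit is 0 or less. Alpha is 0.05, or 0.05/3 for a country. With n infants per arm, the tip lies below 10% of the missing infants once missingness exceeds k/(0.10 × n).

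| Scenario | k at tip | Missing rate above which the tip is below 10% | Tip at 1% missing | at 2% | at 5% | at 10% |
|---|---|---|---|---|---|---|
| Primary, 63 v 159 | 62 | 62/1443 = 4.3% | 43.0% | 21.5% | 8.6% | 4.3% |
| Primary, 50 v 124 | 45 | 45/1443 = 3.1% | 31.2% | 15.6% | 6.2% | 3.1% |
| Country, 21 v 53 | 10 | 10/481 = 2.1% | 20.8% | 10.4% | 4.2% | 2.1% |
| Very severe, 23 v 58 | 15 | 15/1443 = 1.0% | 10.4% | 5.2% | 2.1% | 1.0% |
| 61 events, 17 v 44 | 10 | 10/1443 = 0.7% | 6.9% | 3.5% | 1.4% | 0.7% |

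The last four columns give the tip as a share of the missing nirsevimab infants.

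**What one step does at 5% missing** (about 722 per arm, so 72 added nirsevimab events):
- Primary: 1 − 135/159 = 15% (95% CI −7% to 33%), from 60%.
- Very severe: 1 − 95/58 = −64%, from 60%.
- 61 events: 1 − 89/44 = −102%, from 61%.

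**Mixed pool.** If drop-outs have a 1.1% risk and untested admissions are RSV-positive with share q, the pooled percentage reaches 10% when the untested fraction is (10 − 1.1)/(q − 1.1). That is 8.9/58.9 = 15% for q = 60% and 8.9/78.9 = 11% for q = 80%.

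**The case against.** The strongest reply is that missing data may be too rare for this to matter. Protocol 7.2 expects withdrawal to be uncommon. Protocol 7.3 does not class an infant as lost to follow-up before the 12-month call (24-month for UK reconsented infants), which falls after the 28 February 2023 cut-off. LRTI admissions of withdrawn infants can be retrieved where parents consented. At 1% missing, the primary, country and very severe tips are all at or above 10%, and the grid brackets them. Because arms vary separately, a result that survives 10% on nirsevimab against 0% in control also survives every smaller nirsevimab percentage, with person-time held fixed. A pool with more than about 11% to 15% untested admissions could also plausibly sit at 10% or more. All of this stands.

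A reader might therefore infer too much in two ways. One is that the grid cannot locate any plausible tipping point. The documents do not support this, because the answer depends on the amount and mix of missing data, which they do not state. The other is that this is the only planned check. It is not: all-cause LRTI hospitalization needs no RSV result (SAP 6.6.4.3.1), RSV test status is tabulated by arm (6.6.7.4), and time to discontinuation is compared by arm (6.6.7.5). These bear on the same worry, but none models the effect of informative missingness on RSV efficacy.

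The reply does not remove the point for the two key secondary tests, which reuse the grid at thresholds of about 1.0% and 2.1%, or for an analysis near 61 events. Nor does low missingness answer the pooling problem.

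**Conclusion.** The concern holds in a conditional form. The grid leaves 0% to 10% unexamined, and the tip falls there once missingness per arm passes about 4.3% or 3.1% for the primary endpoint (at the 1.1% and 0.86% rates), 2.1% for a country, 1.0% for very severe disease, or 0.7% with only 61 events. Below those levels, or if the 10% v 0% step is survived, the grid is adequate for drop-outs.

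The thresholds rest on planned rates, 60% efficacy, equal person-time, equal missing numbers per arm, and no events imputed in control. Higher observed efficacy or control imputation would raise them. Separately, one percentage per arm cannot describe both a drop-out and an untested admission, whatever the missing rate. The consequence is limited to how a sensitivity analysis can be read. No confirmatory decision changes.

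**What to change.** Amend SAP 6.6.2.2, and carry the change into 6.6.5.1.2 and 6.6.5.2.2:

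1. Split the missing pool into infants who discontinued and LRTI admissions without an RSV result. For very severe disease, keep admissions with missing oxygen data out of the drop-out group too.
2. For drop-outs, add steps of 1 percentage point or less, or of one event, from 0% to 10%. Take the unobserved time as season end or cut-off minus the censoring date.
3. For untested admissions, vary the RSV-positive share from 0% to 100%, including the share seen among tested admissions, with person-time ending at the recorded admission date.
4. Report the exact tipping value for each endpoint, and keep the best-case and worst-case rows as bounds.

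The cost is SAP wording, reprogramming and a longer output for one sensitivity analysis. The dates and RSV test results are already collected, so no new data are needed.
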